9.3.4 Time From Randomization to Death Due to Any Cause

Time from randomization to death due to any cause (overall survival, OS), is defined as the number of days from randomization to death. The time measured in days, from randomization to death due to any cause, will be analyzed using the Kaplan-Meier estimator of the survival function and the log-rank test of the null hypothesis of equal hazard functions, stratified by age group and region. The p-value of the two-sided log-rank test with significance level of 5% will be presented along with plots of the estimated survival functions for the two treatment groups, stratified by age group and region. The treatment effect of degarelix will be further examined by fitting a stratified Cox regression model for the time to death from any cause. The model will include treatment as a factor, be adjusted for the baseline CV risk factors as appropriate and stratified by age-group and region. The 95% confidence limits and associated p-value for the hazard ratio comparing treatment with degarelix to leuprolide will be presented.

TLF Table: Secondary Endpoint: Time to Death Due to Any Cause – FAS

TLF Figure: Survivor Function for Time to Death Due to Any Cause – FAS

9.3.5 Time from Randomization to confirmed (adjudicated) Cardiovascular-Related Death

Time from randomization to adjudicated CV-related death, is defined as the number of days from randomization to the date of the adjudicated CV-related death. The cause of death will be adjudicated by the external independent CEC Committee. Undetermined deaths will be presumed and analyzed as non-cardiovascular deaths. In order to correctly assess the treatment effect associated with degarelix with respect to the time to CV-related death, it is necessary to account for the competing risk, death due to other causes. The time measured in days, from randomization to the adjudicated CV-related death, will be analyzed using the Nelson-Aalen estimator of the cumulative cause specific hazard function and the log rank test of the null hypothesis of equal cumulative cause specific hazard functions, stratified by age group and region. The p-value of the two-sided log rank test with significance level of 5% will be presented along with plots of the cumulative cause specific hazard functions for the two treatment groups, stratified by age group and region. The treatment effect of degarelix will be further examined by fitting a stratified Cox-type

Page 29 of 51

regression model for the cause specific hazard function associated with CV-related death. The model will include treatment as a factor, be adjusted for the baseline CV risk factors as appropriate and stratified by age-group and region. The 95% confidence limits and associated p-value for the cause specific hazard ratio comparing treatment with degarelix to leuprolide will be presented.

TLF Table: Secondary Endpoint: Time to Adjudicated Cardiovascular-related Death – FAS

TLF Figure: Cumulative Cause Specific Hazard Function for Time to Adjudicated Cardiovascular-related Death – FAS

9.3.6 Time from Randomization to Failure in Progression-Free Survival

Progression-free survival (PFS) is a composite endpoint consisting of the following conditions:

- Death
- Radiographic disease progression defined as one or more new metastatic skeletal lesions observed on bone scan; one or more new metastatic extra-skeletal lesions at least 1.5 cm in greatest dimension visible on computed tomography or magnetic resonance imaging scan as confirmed by the Investigator.
- Introduction of additional therapy related to prostate cancer treatment including radiation, anti-androgens and second-line treatment. (ATC and MedDRA codes for disease progression are included in Appendix 3)
- PSA failure defined as the time from randomization to the second occasion (must be at least two weeks apart from the first and correspond to consecutive measurements) in which the PSA value fulfills the following criteria:
 - I. An absolute increase of ≥ 5 ng/ml above nadir and
 - II. An increase of > 50 % of nadir

Time to PFS failure is therefore defined as the time, measured in days, from randomization to the first occurrence of one of the above composite endpoint criteria. Patients discontinuing from treatment/withdrawn from the study will be censored at the time of discontinuation/withdrawal. Time to PFS failure will be analyzed using the Kaplan-Meier estimator of the survival function, the Cox regression model for the hazard rate and the log-rank test of the null hypothesis of equal hazard functions, stratified by age group and region. The p-value of the two-sided stratified log-rank test with significance level of 5% will be presented along with plots of the estimated survival functions for the two treatment groups, stratified by age group and region. The estimated hazard ratio and the associated 95% confidence interval and p-value comparing the treatment with Degarelix to Leuprolide will also be presented.

TLF Table: Secondary Endpoint: Time to PFS Failure - FAS

TLF Figure: Survivor Function for Time to PFS Failure - FAS

Page 30 of 51

9.3.7 Testosterone levels at day 28, 168 and 336 in patients treated with degarelix and leuprolide

The proportion of patients castrated at day 28, 168 and 336 will be presented by treatment group, along with the number of patients with testosterone measurements at each assessment. Castration is defined as testosterone levels ≤ 0.5 ng/mL. Further, the proportion of patients castrated at both day 28 and 168, as well as at all three visits will be presented along with the number of patients with assessments at each of the corresponding times. For patients discontinuing treatment during the trial, any testosterone data collected after the date of discontinuation will be excluded from the analysis.

TLF Table: Secondary Endpoint: Probability of testosterone levels remaining at castrate levels – FAS

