### **3.5.7 Withdrawal Criteria**

In line with inclusion criterion No. 4 (Section 4.1.1), investigators and patients are encouraged to continue IMP treatment during the entire duration of the trial, unless clinical progression or medical status indicate otherwise at the discretion of the Investigator.

Specific withdrawal criteria and processes for IMP treatment and/or trial discontinuation are described in Section 4.4.

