- b) Stage of prostate cancer should be based on clinical assessment and radiographic imaging (e.g. bone scan, MRI or CT performed as per standard clinical practice at the discretion of the Investigator) and should have been done within 3 months prior to randomization. If no radiographic image is available at the time of screening, a bone scan should be performed as part of the screening procedures. These data must be available for trial documentation before randomization.
- c) The bone scan at the End-of-Trial visit (or End-of-Treatment visit) as part of the PFS endpoint follow-up can be performed up to 7 days before the actual visit.
- d) The IPSS questionnaire should be completed by the patient before the PRO questionnaires DASI, CAQ and EQ-5D-5L.
- e) PRO questionnaires: 1) DASI, 2) CAQ, and 3) EQ-5D-5L. The questionnaires should be completed in the given order.
- f) Health economics: CV-related hospitalization events, CABG/PCI procedures and ER visit events.
- g) ECG, vital signs, blood sampling, and urine collection must be performed prior to dosing. The results from the Screening visit must be available prior to randomization.
- h) Glycemic evaluation at the Screening visit: HbA1c in all patients (fasting not needed). Glycemic evaluation at Visit 2 and at the End-of-Trial visit: plasma glucose and serum insulin. The blood samples must be taken while the patient is in fasting state, i.e. minimum of 8 hours without caloric intake.
- i) Metabolic evaluation: total cholesterol, HDL-cholesterol, low density lipoprotein LDL-cholesterol, triglycerides and uric acid. The blood samples must be taken while the patient is in fasting state, i.e. minimum of 8 hours without caloric intake.
- [REDACTED]
- [REDACTED]
- l) Patients who prematurely discontinue treatment with IMP, or receive prohibited medication (Section 4.3.2), should be called in for an end-of-treatment visit as soon as possible (within 30 days) after a decision of treatment discontinuation has been taken. Following the End-of-Treatment visit, the patient will be followed-up as described in Section 4.4.
- m) Blood sampling for analysis of testosterone and PSA should not be done in patients who have discontinued treatment with IMP and have performed an end-of-treatment visit.

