#### 6.5 End-of-Treatment Visit

Patients who prematurely discontinue treatment with IMP, or receive prohibited medication (Section 4.3.2), should be called in for an end-of-treatment visit as soon as possible (within 30 days) after a decision of treatment discontinuation has been taken.

The following must take place at the End-of-Treatment visit:

- IPSS
- PRO (DASI, CAQ and EQ-5D-5L)
- Health economics (CV-related hospitalization events, CABG/PCI procedures and ER visit events)
- 12-lead ECG
- Vital signs (pulse and blood pressure)
- Blood collection for central laboratory analysis of:
  - Testosterone
  - PSA
  - Clinical chemistry and hematology parameters
  - Glycemic and metabolic parameters (*Note*: The blood samples must be taken while the patient is in fasting state, i.e. minimum of 8 hours without caloric intake.)
- Urinalysis (dipstick)
- Body weight, waist and hip circumference
- [REDACTED]
- Physical examination
- Radiographic imaging (bone scan). (Imaging can be performed up to 7 days before the End-of-Treatment visit.)
- Drug accountability
- Recording of any change in use of concomitant medication

- Recording of adverse events, including CV-related signs
- Inform the patient about the planned follow-up and End-of-Trial visit

Following the End-of-Treatment visit, the patient will be followed-up as described in Section 4.4.

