9.1 General Considerations

The analysis of efficacy will be performed for the FAS (unless otherwise specified). For the purpose of this CV outcome study, patients prematurely discontinuing from treatment will be followed-up for the occurrence of MACE events based on monthly telephone interviews. Unless otherwise stated, time to event endpoints will be censored at the time of treatment discontinuation, initiation of prohibited therapies related to hormonal therapy, lost to follow-up/withdrawal from the study or day 336, whichever occurs first. Initiation of prohibited therapy related to hormonal therapy includes the following:

- Surgical castration or other hormonal manipulation in addition to the IMPs
- Anti-androgens for combined androgen blockade (anti-androgen use for initial flare protection is allowed for a maximum period of up to 28 days after randomization)
- Estrogens
- Megestrol acetate
- Ketoconazole
- Abiraterone
- Enzalutamide
- Any additional hormonal therapy initiated as a combination therapy with the IMP

The associated ATC and MedDRA codes for the above prohibited therapies are provided in Table 11 and Table 12. Hypothesis tests will be two-sided at a significance level of 5% and missing data will not be imputed. 95% confidence limits and the associated p-values will be presented for estimates of the treatment effect comparing degarelix to leuprolide for all regression analyses.

For the purposes of	this trial,		
_			
			•

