Appendix 3 ATC codes and MedDRA terms for disease progression

A list of ATC codes for antiandrogens and additional therapies classified as disease progression are defined below. Please note that the list may be non-extensive.

Table 6 ATC Codes for Antiandrogens

Level 5 codes
L02BB01 Flutamide
L02BB02Nilutamide
L02BB03Bicalutamide
L02BB04Enzalutamide
G03HA01 Cyproterone

Table 7 ATC codes for Additional Therapy

Level 5 codes
L01DB07Mitoxantrone
L01CD02Docetaxel
L01XX11 Estramustine
L01CD01 Paclitaxel
L02AA01 Diethylstilbestrol
L02AA02 Polyestradiol phosphate
L02AA03 Ethinylestradiol
L02AA04 Fosfestrol
L02AB01 Megestrol
L02BG01 Aminoglutethimide
L02BX03 Abiraterone
G01AF11 Ketoconazole

Investigators recording of disease progression are marked as a tick-box on the Adverse Event form in the eCRF. The MedDRA terms to be used for radiation and second line treatment are defined below.

Page 47 of 51

Table 8 MedDRA Codes (preferred terms) for Radiation

10006089	Brachytherapy to prostate	PT
10014442	Electron radiation therapy to prostate	PT
10017683	Gamma radiation therapy to prostate	PT
10034955	Photon radiation therapy to prostate	PT
10061544	Radiotherapy to prostate	PT
10048205	X-ray therapy to prostate	PT
10014435	Electron radiation therapy to bone	PT
10017675	Gamma radiation therapy to bone	PT
10034947	Photon radiation therapy to bone	PT
10062089	Radiotherapy to bone	PT
10048197	X-ray therapy to bone	PT

 Table 9
 MedDRA Codes (preferred terms) for Second Line Treatment

10061916	Prostatectomy	PT
10050756	Radical prostatectomy	PT
10038961	Retro-pubic prostatectomy	PT
10042594	Supra pubic prostatectomy	PT
10044445	Transurethral prostatectomy	PT

The following terms are also to be classified as investigators recording of disease progression, in case the investigator did not check the tick-box, but only recorded the AE.

Table 10 MedDRA Codes (preferred terms) for additional classification of investigators recording of disease progression

10010264	Condition a ggravated	PT
10061818	Disea se progression	PT
10061819	Disea se recurrence	PT
10048669	Terminal state	PT
10051398	Malignant neoplasm progression	PT
10027452	Meta stases to bone	PT
10027459	Meta stases to lymph nodes	PT
10027457	Meta stases to liver	PT
10027458	Meta stases to lung	PT
10027463	Meta stases to pleura	PT
10062194	Metastasis	PT

Page 48 of 51

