Appendix 4 ATC codes and MedDRA terms for Prohibited Therapy

A list of ATC codes for prohibited concomitant medication are defined below. Please note that the list may be non-extensive.

Table 11 ATC codes for prohibited concomitant medication

Level 5 codes
L02AB01 Megestrol a cetate
G01AF11 Ketoconazole
L02BX03 Abiraterone
L02BB04Enzalutamide
L02BB01Flutamide
L02BB02Nilutamide
L02BB03Bicalutamide
G03HA01 Cyproterone
L02AA01 Diethylstilbestrol
L02AA02 Polyestradiol phosphate
L02AA03 Ethinylestradiol
L02AA04 Fosfestrol

Additionally all substances in the ATC G03 therapeutic subgroup are considered as prohibited concomitant medications.

Table 12 MedDRA code (preffered term) for prohibited therapy

10049628 Bilateral orchidectomy	PT
---------------------------------	----

Page 49 of 51

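### SAP 9.3.6 censors PFS at an undefined discontinuation date with no event-over-censoring rule, so progression first documented at or after stopping is normally not counted

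*SAP*

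**What the plan says.** **Event.** SAP 9.3.6 measures PFS "from randomization to the first occurrence of one of the above composite endpoint criteria": death, radiographic progression, additional prostate cancer therapy, or PSA failure dated at the second qualifying value.

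**Censoring.** The same section adds: "Patients discontinuing from treatment/withdrawn from the study will be censored at the time of discontinuation/withdrawal". There is no exception for stopping because of progression. Protocol 9.6.3.7 has no PFS-specific censoring sentence, so the protocol's general default in 9.6.1 applies. SAP 9.1 repeats that default for endpoints without a stated rule of their own: "time to event endpoints will be censored at the time of treatment discontinuation, initiation of prohibited therapies related to hormonal therapy", loss to follow-up or withdrawal, or Day 336.

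**Reasons to stop.** Under Protocol 3.5.7, investigators and patients are "encouraged to continue IMP treatment during the entire duration of the trial, unless clinical progression or medical status indicate otherwise".

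**Assessment after stopping.** Under Protocol 6.5, a patient who stops early "should be called in for an end-of-treatment visit as soon as possible (within 30 days) after a decision of treatment discontinuation has been taken". That visit includes a bone scan and a PSA. Footnote c of Protocol Table 1 gives the scan's purpose: "The bone scan at the End-of-Trial visit (or End-of-Treatment visit) as part of the PFS endpoint follow-up". It may be done up to 7 days before the visit.

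**Drug lists.** SAP Appendix 3 (Tables 6 and 7) states: "A list of ATC codes for antiandrogens and additional therapies classified as disease progression are defined below". SAP Appendix 4 (Table 11) states: "A list of ATC codes for prohibited concomitant medication are defined below".

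**The concern.** Kaplan-Meier, log-rank and Cox methods assume that a censored patient has the same future risk as those still followed. Here one cause of censoring is the outcome itself: the investigator suspects progression, treatment stops, and the confirming scan, PSA, next therapy or death comes afterwards. The protocol collects the scan for PFS, and the SAP then normally places it beyond the censoring date.

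Two gaps add to this. The discontinuation date is undefined in 9.3.6, while SAP section 4 equates going off randomized drug with the last injection. The arms are dosed every 28 and every 84 days, so on that reading the censoring point differs by arm. Also, if the prohibited-therapy default applies to PFS, the start of one drug is both failure and censoring, with no rule to choose between them.

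At stake are the PFS failure rate in each arm and, if stopping or its timing differs by arm, the hazard ratio. SAP 9.2.2.4 lifts this censoring for first adjudicated MACE only, so no planned PFS analysis would show the effect.

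**Working it through.** The documents give no PFS event rate, event count or power, so there is no plan figure to reproduce. The check has three parts.

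**1. What counts under each reading of the discontinuation date.** Take a hypothetical patient (days assumed): stop decision on Day 140 before any injection that day, End-of-Treatment visit and scan with new lesions on Day 155, a Table 7 chemotherapy on Day 170, death on Day 300. By Protocol Table 2 the last injection is Day 112 on degarelix and Day 84 on leuprolide.

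| Date used | Censored, degarelix | Censored, leuprolide | Scan, Day 155 | Therapy, Day 170 | Death, Day 300 |
|---|---|---|---|---|---|
| Last injection (SAP section 4) | 112 | 84 | lost | lost | lost |
| Stop decision | 140 | 140 | lost | lost | lost |
| End-of-Treatment visit | 155 | 155 | tie, no rule | lost | lost |

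This patient meets three PFS criteria, and none is sure to count under any reading. Under the third reading, a scan done before the visit day would count.

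The last-injection date can precede the stop decision by up to about 28 days on degarelix and 84 on leuprolide. Adding up to 30 days to the visit gives 28 + 30 = 58 and 84 + 30 = 114 days, before the ±7-day windows. On this reading, progression documented before the stop decision but after the last injection is lost too, with a longer exposed interval on leuprolide.

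**2. Drug lists.** Table 6 has 5 ATC codes and Table 7 has 12, so 17 PFS-event codes. Table 11 has 12 censoring codes: L02AB01, G01AF11, L02BX03, L02BB01 to L02BB04, G03HA01 and L02AA01 to L02AA04.

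- Table 11 codes also in Tables 6 and 7: 12 of 12.
- PFS-event codes not in Table 11: 17 − 12 = 5 (mitoxantrone, docetaxel, estramustine, paclitaxel, aminoglutethimide).
- Appendix 4 also prohibits the whole ATC G03 group, of which only G03HA01 is on the PFS-event lists.

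**3. Size, by illustration only.** Let p be the true failure probability by Day 336 and f the share of progressors censored before documentation. Both are assumed. With a constant hazard and a short gap, the observed hazard is about (1 − f) times the true one, so the observed failure is about 1 − (1 − p)^(1 − f). For p = 20% and f = 50% this is 1 − 0.8^0.5 = 10.6%. A simulation of 200,000 patients per scenario, with censoring 0 to 30 days before documentation, gave:

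| True p | f = 25% | f = 50% | f = 75% |
|---|---|---|---|
| 10% | 7.6% | 5.1% | 2.6% |
| 20% | 15.4% | 10.6% | 5.5% |
| 30% | 23.5% | 16.6% | 8.6% |

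For the comparison, observed HR ≈ true HR × (1 − f_degarelix)/(1 − f_leuprolide). With equal f the HR is roughly preserved. With a true HR of 1.0 and assumed losses of 40% (degarelix) and 60% (leuprolide), it shows as 0.6/0.4 = 1.50; reversed, 0.4/0.6 = 0.67.

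**The case against.** **Many progressions are documented before stopping.** PSA is drawn at Visits 5, 8 and 11, Protocol 7.2.1.2 allows imaging for suspected metastases during the trial, and Protocol 4.3.1 lets secondary therapy be added on progression. An event dated before the censoring date counts. This stands. A reader might infer that every patient who stops for progression is analysed as progression-free; the text supports that only for progression first documented at or after stopping.

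**SAP 9.3.6 may replace the 9.1 default.** The default yields to a stated rule, and 9.3.6 names only discontinuation and withdrawal. If it replaces the default, a prohibited drug started while still on treatment is simply an event. This is a fair reading, so the drug-list conflict is conditional. The SAP does not say which reading is meant, and Protocol 4.3.2 sends patients given additional hormonal therapy to the End-of-Treatment visit in any case. A reader might also infer that every censoring drug is a PFS event; that holds for the 12 named codes but not for the added G03 group.

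**On-treatment analysis is a legitimate choice.** It matches the trial's general default, and patients also stop for safety, non-compliance or their own reasons. So the censoring is not wholly informative, and it would be too strong to say that the PFS objective cannot be met. But an on-treatment analysis still needs a defined date and a tie rule, and it does not explain scheduling a PFS scan after the point where PFS ends.

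**The size is unknown.** This stands. The documents give no stopping rates by arm or by reason. Open-label sites and different injection schedules make a difference between arms plausible, not established.

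**Conclusion.** The point holds in this form. SAP 9.3.6 censors PFS at a discontinuation date that it does not define and gives no precedence rule. Progression first documented at or after stopping is therefore normally censored as event-free, although the protocol schedules the End-of-Treatment scan for PFS. If the censoring date were the visit itself, the scan and PSA could survive, but later therapy and death would still be lost. Same-day conflict for the 12 Table 11 drugs follows only if the SAP 9.1 default also governs PFS.

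The censoring is partly informative because progression is one reason among several for stopping. It understates PFS failure; it biases the arm comparison only if the share lost differs by arm. The percentages and hazard ratios above rest on assumed inputs and show direction and scale, not an estimate for this trial.

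Severity is should-fix. PFS is a secondary endpoint tested without multiplicity control, and nothing here touches the primary or key secondary conclusions.

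**What to change.** In SAP 9.3.6, replace the censoring sentence with rules that state:

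- PFS is not censored at treatment discontinuation or at the start of prohibited therapy.
- End-of-Treatment findings, additional prostate cancer therapy on its start date, and deaths up to the End-of-Trial visit count as events.
- Anti-androgen for initial flare protection is not an event, as in Protocol 9.6.3.7. The component list in SAP 9.3.6 omits this exception, and Table 6 includes bicalutamide. Protocol 6.3 has flare protection dispensed at Visit 2 to metastatic patients on leuprolide, so without the exception false early failures would gather in that arm.
- An event takes precedence over censoring on the same day.
- Patients without an event are censored at their last PFS assessment or contact.

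Keep the present rule as a labelled supportive on-treatment analysis, with the discontinuation date defined.

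**Cost.** SAP wording and reprogramming of one endpoint. The data are already planned: End-of-Treatment scan and PSA, monthly calls covering concomitant medication, vital-status follow-up, and the End-of-Trial scan. One limit should be stated: PSA is not sampled after an End-of-Treatment visit, so later events can come only from scans, therapies and deaths.
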